8.1.1. Definitions

The following definitions apply to the design of the study:

- **Index date** is defined as the date of the first (non-missing) dose of mepolizumab.
- The **pre-index period** for data collection is defined as up to 12 months prior to the index date.
- **Study period is up to 36 months.** It spans from 12 months before the index date, i.e., for collecting available demographic and relevant medical history prior to the first dose of mepolizumab until the end of the follow-up period.
- **Follow-up period is up to a maximum of 24 months.** Depending on the time point of initiating mepolizumab treatment in relation to the enrolment start date, data will be collected either prospectively and/or retrospectively until 24 months after the index date, or study discontinuation for any reason, or up to 12 months after mepolizumab treatment discontinuation; whichever comes first.

Figure 1 shows the study workflow scenarios in detail for patients who initiated mepolizumab prior to or at enrolment.

Figure 1 Study Workflow Patient Scenarios

8.2. Study Population and Setting

It is planned to include all evaluable paediatric EGPA patients aged 6-17 years who already initiated mepolizumab treatment in the 12 months prior to the enrolment start date or who will initiate mepolizumab treatment after enrolment start date as part of routine clinical care from specialised centres and hospitals known to treat paediatric EGPA patients in Europe. **Note:** The primary analysis will include data for the primary and secondary objectives that are collected prospectively from patients who initiated mepolizumab at or after enrolment start date. The supplement analysis will include data for the primary and secondary objectives that are collected retrospectively for patients who initiated mepolizumab up to 12 months prior to the enrolment start date.

Once the treatment decision has been made, independent from the decision to enrol patients into the study, eligible paediatric EGPA patients will be invited for enrolment by treating physicians affiliated with Investigator sites participating in this study.

The proposed study enrolment period is 5 years, and it is estimated that approximately 10 evaluable paediatric EGPA patients will be enrolled. The feasibility of recruiting 10 patients within the 5-year time period will be evaluated annually. It is planned to follow patients for 24 months after the first dose of mepolizumab.

The total study duration is estimated to be a maximum of 7 years based on a planned study enrolment period of 5 years and a follow-up period of 24 months after the first dose of mepolizumab.

8.2.1. Inclusion Criteria

A patient who meets **all** of the following criteria is eligible for inclusion:

- Written informed assent and parent/caregiver consent
- Male or female, aged 6 to 17 years at the start of mepolizumab treatment
- Confirmed diagnosis of EGPA
- Initiated mepolizumab up to 12 months prior to enrolment start date (regardless of whether they continue treatment following study enrolment or not) or scheduled to receive treatment with mepolizumab at or after enrolment per routine clinical care

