3.5. Study Population

The study will include paediatric EGPA patients treated with mepolizumab as part of routine clinical care from sites in selected countries in Europe.

Inclusion Criteria:

A patient who meets **all** of the following criteria is eligible for inclusion:

- Written informed assent and parent/caregiver consent
- Male or female, aged 6 to 17 years at the start of mepolizumab treatment
- Confirmed diagnosis of EGPA
- Initiated mepolizumab up to 12 months prior to enrolment start date (regardless of whether they continue treatment following study enrolment or not) or scheduled to receive treatment with mepolizumab at or after enrolment per routine clinical care.

Exclusion Criteria:

A patient who meets **any** of the following criteria is not eligible for inclusion:

- Concurrent enrolment and/or participation in an interventional clinical trial involving either an investigational medicinal product or medical device
- Received treatment with mepolizumab more than 12 months prior to enrolment start date
- Received other biologics within 3 months of the first dose of mepolizumab.

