5. MILESTONES

Enrolment start date: Data collection will start at the time of study enrolment of the first patient into the study from Q4 2022.

Index date: Data will be extracted from medical records by the Investigator or their designee and entered in the eCRF throughout a maximum of 24 months follow-up from the first dose of mepolizumab which is defined as index date.

Study progress: Reports will be developed annually; expected timelines are provided in the table below.

Study end: Data collection will continue until the end of the study (7 years), until target enrolment is achieved of approximately 10 evaluable paediatric EGPA patients, or until early study closure (due to low recruitment rates or insufficient data availability).

Milestone	Planned date
Start of data collection	Q4 2022
End of data collection	Q3 2029
Study progress report 1	Q4 2023
Study progress report 2	Q4 2024
Study progress report 3	Q4 2025
Study progress report 4	Q4 2026
Study progress report 5	Q4 2027
Study progress report 6	Q4 2028
Registration in the EU PAS register	Q4 2022
Final report of study results	By Q4 2029

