8. RESEARCH METHODS

8.1. Study Design

This multinational, multi-site, case-series will aim to collect data on real-world safety and effectiveness up to 24 months after the initiation of mepolizumab treatment in paediatric EGPA patients in Europe. In addition, demographic and relevant medical history data will be collected up to 12 months prior to the first dose of mepolizumab.

EGPA in a paediatric population is extremely rare, and there will be challenges in identifying and recruiting eligible patients. The study design reflects these challenges. All eligible paediatric EGPA patients aged 6-17 years who initiated mepolizumab in the 12 months prior to the enrolment start date (regardless of whether they continue treatment following study enrolment or not), or who will initiate mepolizumab treatment at or after the enrolment start date will be invited for study enrolment by their treating physicians. These physicians will be from specialised centres and hospitals known to treat paediatric EGPA patients from selected countries in Europe. As the study is non-interventional, the decision to treat paediatric EGPA patients with mepolizumab will be made prior to and

independent from the decision to enrol patients into the study, and baseline and follow-up assessments will be in accordance with local standard medical care.

Per the local regulatory requirements, informed consent for minors (defined by the country law) will be obtained from the parent/caregiver with confirmation (assent) from the minor that he/she wishes to participate before enrolment into the study.

After obtaining informed consent from parents/caregivers and assent from paediatric patients, they will be enrolled into the study and data will be extracted from medical records and entered in an eCRF, where applicable.

Depending on the time point of the initiation of mepolizumab treatment in relation to the enrolment start date (i.e., the study start date), data for the primary and secondary objectives will be collected either prospectively (primary analysis) and/or retrospectively (supplemental analysis).

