8.8.4. Study Monitoring

Participating sites will be queried every 12 months from study start to check for newly diagnosed paediatric EGPA patients who initiated treatment with mepolizumab in the previous 12 months.

Patient data will be monitored remotely. Monitoring visits may be scheduled throughout the study, if needed. Monitoring visits will be scheduled in advance, to ensure that the investigator has sufficient time to meet with the SMA and discuss all relevant findings. Patient data will be reviewed and/or audited, and all deficiencies corrected on site, if possible. A complete audit trail of all monitoring visits and data changes will be maintained. A virtual close-out visit will be scheduled when all documents and data have been collected, reviewed and necessary data changes have been made after the last study visit within routine care for the last patient. If the study is terminated, a virtual study close-out visit may be scheduled with the site if needed to retrieve all remaining study records. As long as COVID-19 restrictions apply, on-site study initiation and monitoring visits will not be scheduled until restrictions are alleviated.

The SMA will review the study conduct to determine compliance with the study protocol. The SMA will review and/or audit the electronic forms and source documents to ensure the accuracy and completeness of the data captured for the study. The SMA will review the informed patient assent and parent/caregiver consent forms (ICFs) to ensure that no forms were signed prior to the date of IRB approval of the study. The system for record-keeping will be reviewed.

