8.9. Limitations of the Research Methods

8.9.1. Selection Bias

All eligible paediatric EGPA patients treated with mepolizumab from sites in Europe will be invited for study enrolment including patients who discontinued mepolizumab treatment before enrolment to reduce selection bias. Reasons for patient non-

participation, withdrawal or loss-to-follow-up will be recorded in the eCRF, if available, to address any remaining selection bias.

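### As worded, inclusion criterion 4 has no place for a patient who starts mepolizumab after the enrolment start date and stops before enrolling, contrary to sections 8.1, 8.2 and 8.9.1

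*Protocol*

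**What the plan says.** Section 8.2.1 (repeated in 3.5) offers two ways to meet the fourth inclusion criterion.

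- First part: "Initiated mepolizumab up to 12 months prior to enrolment start date (regardless of whether they continue treatment following study enrolment or not").
- Second part: "or scheduled to receive treatment with mepolizumab at or after enrolment per routine clinical care".

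The first part is tied to one calendar date for the whole study. Section 8.1 equates the two terms: "enrolment start date (i.e., the study start date"). The milestones place that date at the first patient's enrolment: "Data collection will start at the time of study enrolment of the first patient into the study from Q4 2022". The second part speaks only of enrolment and has no wording about patients who have stopped.

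Three other sections describe who is meant to be in the study:

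- Section 8.1 says that patients "who will initiate mepolizumab treatment at or after the enrolment start date will be invited for study enrolment by their treating physicians". Section 8.2 likewise covers all who start after that date.
- Section 8.9.1 counters selection bias by inviting all eligible patients, "including patients who discontinued mepolizumab treatment before enrolment to reduce selection bias".
- Section 8.8.4 has sites "queried every 12 months from study start to check for newly diagnosed paediatric EGPA patients" who began mepolizumab in the preceding 12 months.

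**The concern.** Sites apply the numbered criteria. Within one sentence the criterion moves from the study's enrolment start date to enrolment, and the protection for patients who have stopped stays with the first part only. Someone whose first dose falls after the study has opened but before their own enrolment depends entirely on the second part. If that patient has already stopped, nothing remains scheduled.

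The patients at risk would belong to the primary analysis, which section 8.7.2 defines by a start at or after the enrolment start date, and the primary objective is safety. A patient who stopped early because of an adverse event or lack of benefit may be among the most informative cases. Losing such patients through a wording conflict would undo the safeguard in 8.9.1.

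A related mismatch is in 8.8.4. The query is limited to newly diagnosed patients, whereas eligibility asks only for a confirmed diagnosis, and section 8.3.2 records relapsing or refractory status at the index date. A child diagnosed earlier who newly starts mepolizumab is eligible but outside the query as worded.

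**Working it through.** **Inputs** (months from the enrolment start date, month 0)

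- Intended population: first dose at month −12 or later (8.1, 8.2).
- First part of the criterion: first dose in the 12 months before month 0, continuing or not (8.2.1).
- Second part: scheduled to receive treatment at or after enrolment (8.2.1), taken here as the patient's own enrolment.
- Site query: every 12 months from study start, looking back 12 months (8.8.4).
- Planned number: about 10 of at most 13 patients over five years (8.5). This is a feasibility estimate (10/13 = 77%, 10/5 = 2 a year), so there is no formula to reproduce.

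**Rules.** Let s be the month of first dose, e the month of own enrolment and x the month of stopping.

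- Intended: s ≥ −12.
- First part: −12 ≤ s < 0.
- Second part, *initiate* reading (scheduled to start): s ≥ e. Section 8.7.1.1 supports it by describing enrolled patients as scheduled to initiate after enrolment.
- Second part, *receive* reading (further doses due): no stop, or x > e.

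**Test cases**

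| s | e | x | Intended | Criterion, *initiate* reading | Criterion, *receive* reading |
|---|---|---|---|---|---|
| −6 | 3 | none | yes | yes | yes |
| −6 | 3 | 1 | yes | yes | yes |
| 14 | 13 | none | yes | yes | yes |
| 14 | 14 | none | yes | yes | yes |
| 14 | 24 | none | yes | **no** | yes |
| 14 | 24 | 20 | yes | **no** | **no** |

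The second and last rows both describe a patient who stopped before enrolling. One is eligible and the other is not, and what separates them is whether the first dose came before or after month 0. The exclusion criteria neither cause nor close the gap.

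**Annual query.** Queries at months 12, 24, 36, 48 and 60 cover starts in months 0–12, 12–24, 24–36, 36–48 and 48–60. None of these windows overlaps −12 to 0, so nobody found by these queries can qualify under the first part. (A query sent at month 0 itself would look back over the first-part window; the protocol does not say whether there is one.) Everyone found has already started, and therefore depends on how the second part is read.

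**Size.** One case in 10 is 1/10 = 10% of the series. The protocol does not give the share of patients identified after their first dose or the share who stop before enrolling. To show scale only, assume 25% to 100% are identified late and 10% to 30% of those have stopped:

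- *Initiate* reading: 10 × 0.25 = 2.5 to 10 × 1.00 = 10 patients excluded.
- *Receive* reading: 10 × 0.25 × 0.10 = 0.25 to 10 × 1.00 × 0.30 = 3 patients excluded.

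The width of these ranges shows that the number cannot be settled from the document.

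**After rewording.** If the second part is tied to month 0 and applies whether or not treatment continues, every row of the table is eligible, in line with 8.1, 8.2 and 8.9.1.

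**The case against.** The strongest reply is that the intent is plain. Sections 3.4, 8.1 and 8.2 cover everyone who starts at or after the enrolment start date, and 8.9.1 names patients who discontinued. The protocol also uses enrolment loosely elsewhere: 8.9.2 pairs a start at or after enrolment with a start before the study start date, and 8.3.4.3, 8.3.4.5, 8.3.4.6 and 10.3 speak of 12 months before enrolment. If the second part uses the same shorthand, much of the gap closes. Figure 1, which could not be read here, may also show this group. This stands as evidence of intent: it is a drafting conflict, not a deliberate exclusion. It does not rescue the criterion, because the same sentence uses the full term for the first part and only the short one for the second.

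A reader might infer that the criterion both excludes everyone who starts after study opening and removes early stoppers selectively. The documents do not support both at once. On the *initiate* reading the loss covers all patients identified after their first dose, so it is not selective. On the *receive* reading only those who stopped are lost. Early stoppers are the one group lost on both.

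A reader might also treat the annual query as the route of recruitment and derive a typical delay from it. Sections 8.1 and 8.2 have treating physicians invite patients once the treatment decision is made; the query is a monitoring check. For the same reason, falling outside the newly-diagnosed query does not mean being missed by the study.

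Nor should the harm be stated as a shifted event proportion. Section 8.7 describes patients one by one and does not summarise across them, so what is lost is a case report.

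**Conclusion.** The criterion contradicts 8.1, 8.2 and 8.9.1. If enrolment in its second part means the patient's own enrolment, a patient who starts after the enrolment start date and stops before enrolling is ineligible on either reading of *scheduled to receive*. If that phrase means scheduled to initiate, patients still on treatment who are identified after their first dose are ineligible too, and patients who have already started are the ones the 8.8.4 query looks for.

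How many patients this affects is unknown. Each is about one tenth of the planned series. A favourable distortion is possible, not established: it requires that early stops are related to adverse events or lack of effect, and stops for other reasons would be lost as well. Because the affected patients belong to the primary safety case series, the wording should be settled rather than left to each site.

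**What to change.** 1. In 3.5 and 8.2.1, replace the second part with: *or initiated, or is scheduled to initiate, mepolizumab on or after the enrolment start date, regardless of whether treatment is continuing at enrolment*.
2. Reconcile enrolment with enrolment start date in 8.3.4.3, 8.3.4.5, 8.3.4.6, 8.9.2 and 10.3.
3. Keep describing these patients' pre-enrolment follow-up as retrospective, as 8.7.2.1 and 8.7.2.2 do. Reconcile this with 8.2 and 8.7.2, which call the primary analysis prospective, and with 3.9, which splits the data at the enrolment start date instead of at enrolment.
4. In 8.8.4, delete the newly-diagnosed limit so that the query covers every paediatric EGPA patient who started mepolizumab in the look-back period, whatever the date of diagnosis.

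The cost is protocol wording and a slightly broader site query. The downside is a few more patients whose on-treatment data are partly or wholly retrospective, and so possibly less complete, as 8.9.2 already acknowledges for pre-enrolment records. Describing those data separately keeps the difference visible.

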8.2.2. Exclusion criteria

A patient who meets **any** of the following criteria is not eligible for inclusion:

- Concurrent enrolment and/or participation in an interventional clinical trial involving either an investigational medicinal product or medical device
- Received treatment with mepolizumab more than 12 months prior to enrolment start date
- Received other biologics within 3 months of the first dose of mepolizumab.

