8.7.1. Analysis Populations

8.7.1.1. Enrolled Population (EP)

The EP will consist of all patients for whom written informed assent as well as written informed consent from parents/caregivers has been obtained. The EP will be used to assess reasons for not initiating mepolizumab while being scheduled to initiate mepolizumab after enrolment.

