9. PROTECTION OF HUMAN SUBJECTS

9.1. Ethical Approval and Subject Consent

The study will be conducted in accordance with ethical principles founded in the Declaration of Helsinki (version 2008) and applicable legal and regulatory requirements and related guidances, especially Directive 2001/83/EC, Regulation (EC) No 726/2004 (REG) and Commission Implementing Regulation (EU) No 520/2012 (IR) as detailed in Good Pharmacovigilance Practices (GVP) Modules V, VI and VIII.

It is the responsibility of GSK and the Investigators to have prospective approval of the study protocol, protocol amendments, and other relevant documents (e.g., ICFs), if applicable, from the IRB/IEC/Competent Authorities. Any necessary extensions or renewals of IRB approval must be obtained for changes to the study such as amendments to the protocol, the ICF, or other study documentation.

Per the local regulatory requirements, informed consent for minors (defined by the country law) will be obtained from the parent/caregiver with confirmation (assent) from the minor that he/she wishes to participate before enrolment into the study. Each investigator will ensure that each patient is given full and adequate oral and written information in the local language about the nature and purpose of the study. The patient will be given the opportunity to ask questions and allowed time to consider the information provided. All parties will ensure protection of patient personal data and will not include names on any sponsor forms, reports, publications, or in any other disclosures, except where required by the local laws and regulations. The signed and dated informed parent/caregiver consent and patient assent forms must be obtained before any data is entered into the eCRF. The investigator must store the original, signed forms. A copy of the signed forms must be given to the patients and parents/caregivers. If the patient decides not to participate, the reason will be collected in the eCRF.

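### For children enrolled after their first dose, entry to the safety series depends on surviving to consent and, on one reading of exclusion 3, on not switching biologic early

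*Protocol*

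**What the plan says.** All references are to the Protocol.

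- **Late entry is allowed.** Section 8.2.1 admits children who "Initiated mepolizumab up to 12 months prior to enrolment start date (regardless of whether they continue treatment following study enrolment or not". Age is fixed at treatment start: "Male or female, aged 6 to 17 years at the start of mepolizumab treatment". Under Section 8.8.4, sites are asked every 12 months about newly diagnosed children who have already started treatment.
- **Consent controls every analysis set.** The first inclusion criterion is "Written informed assent and parent/caregiver consent". Section 8.7.1.1 states: "The EP will consist of all patients for whom written informed assent as well as written informed consent from parents/caregivers has been obtained". Section 8.7.1.2 makes the Safety Population a subset of that group.
- **Exclusion 3** (Section 8.2.2) is "Received other biologics within 3 months of the first dose of mepolizumab", with neither before nor after specified.
- **Selection bias.** Section 8.9.1 says all eligible treated patients are invited, "including patients who discontinued mepolizumab treatment before enrolment to reduce selection bias", and that reasons for non-participation go into the eCRF where available.
- **Data entry.** Section 9.1 states: "The signed and dated informed parent/caregiver consent and patient assent forms must be obtained before any data is entered into the eCRF". It later adds: "If the patient decides not to participate, the reason will be collected in the eCRF".

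**The concern.** Safety is the primary objective, and about 10 children are expected. Section 6.1.1 says mortality in paediatric EGPA is higher than in adult-onset disease, and Section 10.3 asks for every death in the study period whatever its cause. Death is therefore an outcome the study means to capture.

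Where a child can be enrolled months after the first dose, any condition that must hold between first dose and consent acts on outcomes. Surviving to consent is one such condition. Not having received another biologic is a second, if exclusion 3 covers the period after the dose. A child lost in either way leaves no case report. Unless treated children who were not enrolled are counted, a reader of the final report could not tell whether this had happened. Section 8.9.1 does not mention it.

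**Working it through.** **The plan's own figure.** Section 8.5 expects about 10 participants from at most 13 identified, that is 10/13 = 77%. This is a feasibility estimate, so there is no sample-size formula to reproduce. The point rests mainly on reading the sections together.

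**1. Who is exposed.** A child consented at or before the first dose has no gap and is unaffected. Those who started before the enrolment start date (the supplemental analysis) all have a gap. A primary-analysis child can have one too. Sections 8.2 and 8.7.2 define that analysis by starting at or after the study-level enrolment start date, not after the child's own consent, and the 12-month site query looks back at children already treated.

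**2. Death before consent.** Assent plus parental consent is needed for inclusion, for both populations and for any eCRF entry. No waiver or other route for a deceased child is written. A treated child who dies in the gap cannot appear.

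**3. Exclusion 3, two readings.**
- Window before the first dose only: a washout, fixed at baseline, with no selection on outcome.
- Window on both sides: a child enrolled late who received another biologic 2 months after the first dose is ineligible because of what happened on treatment. That works against the aim of Section 8.9.1.

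The text does not choose. The preceding exclusion criterion does give a direction (prior to the enrolment start date).

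**4. The record of non-participants.** Section 9.1 bars any eCRF entry before signed forms, then sends the reason of a patient who declines to the eCRF. The two sentences cannot both be followed as written.

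**5. Adult at enrolment.** Turning 18 does not fail the age criterion. However, Sections 8.1, 8.2.1 and 9.1 describe only parental consent with a minor's assent.

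**6. Scale.** The documents give no early death rate, switch rate or consent lag, so everything here is assumed. Let q be the 12-month risk of death after first dose under a constant hazard, and L the months from first dose to consent, the same for all. Expected missing per 10 treated children = 10 × [1 − (1 − q)^(L/12)].

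| q | L = 3 | L = 6 | L = 12 |
|---|---|---|---|
| 5% | 0.13 | 0.25 | 0.50 |
| 10% | 0.26 | 0.51 | 1.00 |
| 20% | 0.54 | 1.06 | 2.00 |

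With L = 0 the loss is zero. With lags spread evenly over 0 to 12 months, about half of first-year deaths fall before consent. If q is instead the 12-month risk of receiving another biologic, the two-sided window catches only the first 3 months, so the L = 3 column (0.13 to 0.54) is the ceiling.

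The loss of numbers matters little in itself. With no events, the exact one-sided 95% upper bound 1 − 0.05^(1/n) is 25.9% at n = 10 and 28.3% at n = 9. What matters is which child is missing.

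For coming of age, assume ages uniform from 6 to under 18 (144 months). The affected share is L/144: 6/144 = 4.2% (0.42 of 10) and 12/144 = 8.3% (0.83 of 10).

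**The case against.** The case on the other side has real weight.

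- **Exclusion 3 is probably a washout.** It also applies to children only scheduled to start, for whom a post-dose condition could not be checked at entry. This stands as far as it goes: the defect is a missing direction, not a rule that plainly looks forward.
- **A reader might infer that early failures in general drop out.** The documents do not support that. A child who stopped for an adverse event or lack of effect remains eligible under Section 8.2.1. Even on the two-sided reading, only one who also received another biologic within 3 months is lost.
- **A reader might call this a contradiction of Section 8.9.1.** That section promises invitation to eligible patients, so the two-sided reading defeats its aim but not its letter.
- **Any study needing individual consent loses those who die first.** True, and whether a waiver is possible depends on national law. Section 8.2 also has patients invited once the treatment decision is made, which limits the gap. The supplemental group is presented separately. These points limit the reach, but they do not replace a count of the children lost or a stated limitation.
- **The eCRF sentences may be a drafting slip.** Section 9.1 may intend an exception for refusers. If so, it needs saying. Even then, no count of children treated or dead before consent is required.
- **Turning 18 is unrelated to outcome.** Agreed. It is a gap in the consent wording and is no evidence of lost failures or deaths.

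**Conclusion.** The point holds for children enrolled after their first dose: all of the supplemental group, and any primary-analysis child who consents after starting. For them, entry is conditional on surviving to consent, and the protocol neither counts those lost nor names the limitation. Exclusion 3 is ambiguous and, on one literal reading, adds an outcome-based exclusion. Section 9.1 must be reconciled with itself. The missing consent route for patients now adult is a separate, administrative gap.

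The size is unknown. The illustration runs from 0 to 2 deaths missed per 10 treated children, depending wholly on assumed risk and lag; its upper end needs a 20% first-year risk and every child consenting 12 months late. A reader might turn one missing child into 10% of the series. The documents do not support that as a predicted loss: they give no event rate, the 10 are patients already assumed willing, and Section 8.7 plans no summary across patients. The conclusion rests on the wording of eligibility, consent and population definitions, which belong in the protocol, and not on any of these figures.

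**What to change.** 1. Word exclusion 3 so that it looks only at the period before the first dose, or confirm in the text that this is what is meant.
2. In Section 8.2.1, the EP definition and Section 9.1, allow the patient's own consent if of legal age. Where local law and the ethics committee permit, allow inclusion of deceased patients.
3. Replace the eCRF entry for non-participants with an anonymous site log of treated, eligible, invited, declined and died-before-consent counts, tabulated in the final report.
4. Report time from first dose to consent for each patient.
5. Name survival to consent as a limitation in Section 8.9.1.

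The cost is a few words in the criteria, consent wording in the ethics submission and a short log at each site. Some countries may allow only the count for deceased patients, but the count alone would show whether selection had occurred.
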